3.2 Secondary endpoints

3.2.1 Objectives:

This study will seek to establish whether TNM™ treatments provide adjuvant therapeutic effectiveness beyond that observed with dopamine replacement therapies (DRTs) to (1) provide global benefits, (2) improve activities of daily living related to motor function, (3) provide clinically meaningful change (4) improve motor symptoms and (5) improve quality of life (QoL) for participants with PD.

3.2.2 Endpoints:

- The combined measure of MDS-UPDRS Parts I, II, and III– a measure of the global impact of PD across diverse domains (i.e., summed score from the MDS-UPDRS Parts I, II and III)
- MDS-UPDRS II – patient reported evaluation of activities of daily living relating to motor function
- CGI-I - clinician assessment in how much the patient's illness has improved or

- worsened relative to a baseline state at the beginning of the intervention; may also be referred to as the overall CGI-I
- MDS-UPDRS III - clinician-scored motor exam
 - the Parkinson's Disease Questionnaire 39 summary index score (PDQ-39SI) – quality of life measure that assesses how often people living with PD are affected across 8 dimensions of daily living

3.3 Safety endpoints:

3.3.1 Objectives:

This study will seek to establish the safety of TNM™ by monitoring adverse events and by evaluating whether TNM™ is associated with a worsening of balance, functional mobility and gait in participants with Parkinson's disease.

3.3.2 Endpoints:

- AE frequency
- mini-BESTest – a performance-based measure of dynamic balance, functional mobility and gait

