Phone contact – day 15 (+/- 1 day): The study coordinator will call the participant at the scheduled time, to ask if the participant has experienced any adverse events or changed any medications since the start of the study. Study sites are encouraged to have continuous communication with the study participant and study partner outside of the defined protocol visits, in the manner most accommodating to them, to assist with rapport, retention, and the identification of medication changes or adverse events in real-time.

Baseline Patient reported outcomes – day 28 (+/- 1 day): The study coordinator will call the participant at the scheduled time to ask if the participant has experienced any adverse events or changed any medications since the start of the study. They will then ask participants to complete the ePROs at a time when they are in an on-state:

- PDQ-39
- MDS-UPDRS Part II

- FACIT-F
- GDS
- PAS
- PDSS-2
- ESS

Baseline 2 (in clinic) – day 29 (+/- 3 days):

The randomization activities should be performed per the SOE in the appendix. The collection of MDS-UPDRS Part III data should begin 30-90 minutes after time of the last DRT dose, with participant confirmation of on-state. The timing of the administration of the MDS-UPDRS Part III from dose should be recorded and kept consistent at each administration of the assessment for that participant.

- Concomitant medication and adverse event review
- MDS-UPDRS Part III with video (captured using the Machine Medicine Kelvin software)
- mini-BESTest
- 10m TUG (Encephalog™)
- MDS-UPDRS I
- Ear exam
- Weight
- Pregnancy test, as required
- MDS-NMS (including the Non-Motor Fluctuations Subscale)
- MoCA v8.2
- CGI baseline interview (overall and focused)
- oSDMT
- Modified Schwab & England
- UPDRS I
- UPDRS IV
- PRO-PD
- Zarit Burden Interview
- Review of inclusion/exclusion criteria

The participant should be fitted, and the device adjusted as necessary with the ear pad selection documented. Participants should confirm that they find wearing the unpowered device to be comfortable enough to proceed with the study treatment prior to randomization. If they do not, the reason for screen failure should be noted in the study documentation.

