 - MDS-UPDRS Part II
 - GDS
 - PAS
 - PDSS-2
 - ESS
 - FACIT-F
 - ii. In clinic visit (day 113 +/- 3 days)
 - Concomitant medication and adverse event review
 - MDS-UPDRS Part III with video (captured using the Machine Medicine Kelvin software). *The timing of the administration of the MDS-UPDRS Part III from last DRT dose should be recorded and*

Clinician version – not for patient use

kept consistent with the timing from last dose to administration as noted in the BL2 visit. Administration must occur within 30 – 90 minutes after last dose.

- Mini-BESTest
- 10m TUG (Encephalog™)
- MDS-UPDRS Part I
- MDS-NMS (includes the NMF subscale)
- CGI-I (overall and focused)
- S&E
- Ear exam
- MoCA v8.3
- UPDRS I
- UPDRS IV
- PRO-PD
- Zarit Burden Interview
- Device Usability Questionnaire
- Conduct weight measurement
- Device return and supply return

After the completion of study assessments, participants will be offered the opportunity to consent to the OLE of the study. Participants will not be made aware of their allocation during the RCT portion of the study at any point. Used Devices will be promptly shipped back to the distributor using the Device Return form.

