1.2 STEM-PD OLE

STEM-PD OLE																						
Assessment	Baseline OLE Study Center	PC	PR O (+/- 1 day)	TX1 Virtual (+/- 3 days)	PC	PR O (+/- 1 day)	TX2 Virtual (+/- 3 days)	PC	PR O (+/- 1 day)	EOT1 Study Center (+/- 3 days)	PC	PR O (+/- 1 day)	FU 1 Virtual (+/- 3 days)	PC	PR O (+/- 1 day)	FU 2 Virtual (+/- 3 days)	PC	PR O (+/- 1 day)	FU3 Study Center (+/- 3 days)	PC	PR O (+/- 1 day)	EOT 2 Study Center (+/- 3 days)
Day	113 (+/- 3 days)	127 (+/- 1 day)	140 (+/- 1 day)	141 (+/- 3 days)	155 (+/- 1 day)	168 (+/- 1 day)	169 (+/- 3 days)	183 (+/- 1 day)	196 (+/- 1 day)	197 (+/- 3 days)	211 (+/- 1 day)	224 (+/- 1 day)	225 (+/- 3 days)	239 & 253 (+/- 1 day)	266 (+/- 1 day)	267 (+/- 3 days)	281 & 295 (+/- 1 day)	308 (+/- 1 day)	309 (+/- 3 days)	323 & 337 & 351 (+/- 1 day)	364 (+/- 1 day)	365 (+/- 3 days)
Informed Consent	X																					
Med Hx and ConMed Hx Review	X																					
Ear Exam										X									X			X
PGI-I										X												
Weight										X									X			X
MoCA										X									X			X
MDS-NMS				X			X			X			X			X			X			X
MDS-UPDRS I										X												
UPDRS I										X												
MDS-UPDRS II			X			X			X			X			X			X			X	
MDS-UPDRS III (on-state)				X			X			X			X			X			X			X
Mini-BESTest										X									X			X

STEM-PD, V6.0 -- CONFIDENTIAL

Clinician version – not for patient use

STEM-PD OLE																						
Assessment	Baseline OLE Study Center	PC	PR O	TX1 Virtual	PC	PR O	TX2 Virtual	PC	PR O	EOT1 Study Center	PC	PR O	FU 1 Virtual	PC	PR O	FU 2 Virtual	PC	PR O	FU3 Study Center	PC	PR O	EOT 2 Study Center
Day	113 (+/- 3 days)	127 (+/- 1 day)	140 (+/- 1 day)	141 (+/- 3 days)	155 (+/- 1 day)	168 (+/- 1 day)	169 (+/- 3 days)	183 (+/- 1 day)	196 (+/- 1 day)	197 (+/- 3 days)	211 (+/- 1 day)	224 (+/- 1 day)	225 (+/- 3 days)	239 & 253 (+/- 1 day)	266 (+/- 1 day)	267 (+/- 3 days)	281 & 295 (+/- 1 day)	308 (+/- 1 day)	309 (+/- 3 days)	323 337 & 351 (+/- 1 day)	364 (+/- 1 day)	365 (+/- 3 days)
10m TUG										X												
3m TUG & Finger tapping (Encephalog™ tests)	-----X*-----																					
PDQ-39			X			X			X			X			X			X			X	
Modified Schwab & England										X									X			X
Pro-PD										X									X			X
oSDMT										X									X			X
PDSS-2									X									X			X	
ESS									X									X			X	
PAS									X									X			X	
FACIT-F									X									X			X	
GDS									X									X			X	
CGI-I overall and focused)										X												X
UPDRS IV										X									X			X

STEM-PD, V6.0 -- CONFIDENTIAL

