7.4. DEFINITIONS

Study groups: The group/cohort that originally received passive treatment during the RCT will be referred to as the passive-active group. The group/cohort that originally received active tvCVS treatment during the RCT will be referred to as the active-active group.

Study day: The study day will be calculated in reference to the date of the first baseline virtual visit during the RCT (Day 0). Although the informed consent for the OLE will be completed on day 113, plus or minus window days, because the RCT and OLE are part of the same protocol and the evaluation of effectiveness in the OLE depends on RCT data, all dates in this OLE SAP will be in reference to the first RCT visit (Day 0) as is specified in the protocol.

Analysis day: The analysis day will be calculated in reference to the date of the last assessment in RCT/first assessment in OLE (Day 113). Analysis day will be utilized for comparisons for passive-active participants.

OLE Baseline value: Values obtained at the End of Treatment (EOT) visit for the RCT will define the OLE baseline values. Values obtained at the most recent visit during the RCT will define the OLE baseline values in cases where data is missing for the EOT visit for the RCT.

Adherence (%): Adherence is defined as the total number of times subjects used the device in a given treatment period divided by twice the number of days the subject participated in that treatment period, multiplied by 100 to give a percentage.

Duration of Follow-up: The duration of follow-up will be defined as the number of days from the OLE Baseline until the End of Treatment period 2 (day 365) assessment or the last completed visit (phone call, virtual or in clinic).

Adverse Event:

Per protocol, an AE is any untoward medical occurrence, unintended disease or injury, or untoward clinical signs (including abnormal laboratory findings) in participants, users, or other persons, whether or not related to the investigational medical device. This definition includes events related to the investigational medical device and the events related to the procedures involved. For purposes of analyses, any AE specified on the Adverse Events eCRF page is considered an AE.

Adverse Device Effect (ADE):

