7.8.4.1. Combined measure of MDS-UPDRS Parts I, II, and III (sum score)

This endpoint will evaluate the change in the combined measure of MDS-UPDRS Parts I, II and III. The combined measure of MDS-UPDRS Parts I, II, III will be calculated, inclusive of imputation, as described in SAP v6.0 for RCT Study (Appendix 1). For the passive-active group, the change from corresponding baseline to end of treatment

period will be evaluated using a MMRM model similar to the one described for the primary analysis. Treatment differences will be assessed based on the least-squares mean change scores between the passive and active treatments. Changes meeting or exceeding the previously established MCID for this measure (-6.7 points for clinical improvement)⁸ will be considered clinically meaningful.

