7.8.4.3. Overall CGI-I

The CGI-I provides a clinician's determination of overall change as it relates to all aspects of Parkinson's disease. For ease of interpretation, the CGI-I score will be converted by the following formula: Converted CGI-I = 4 - CGI-I. Thus a 0 corresponds to no change, higher magnitude positive values correspond to greater improvements and higher magnitude negative scores correspond to increased worsening. For the passive-active group, treatment differences will be modeled utilizing the MMRM with no effect for visit as described previously. The effect of the device in the OLE will be considered clinically significant if converted CGI-I scores after active tvCVS during the OLE are statistically significantly greater to those after passive treatment in the RCT.

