7.7.2.2. Overall CGI-I

This endpoint will evaluate the CGI-I score at the end of the treatment period (day 113) which is defined based on change relative to baseline evaluation at day 29. This CGI-I provides a clinician's determination of overall change as it relates to all aspects of PD. For ease of interpretation, the CGI-I score will be converted using the following formula: Converted CGI-I = 4 - CGI-I. Thus a 0 corresponds to no change, higher magnitude positive values correspond to greater improvements and higher magnitude negative scores correspond to increased worsening. To allow for an effect of site, treatment differences will be modeled utilizing the MMRM with no effect for visit as described previously. If the active treatment arm demonstrates converted CGI-I scores that are statistically significantly greater than those in the passive treatment arm, these results would further support the clinical meaningfulness of change due to tvCVS.

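### The reference state for the day-197 CGI-I is undefined; if it is day 29, the OLE test asks whether there was any further change, not whether active-period change exceeded passive-period change

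*SAP*

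**What the plan says.** **Reference interview.** Protocol 4.1.1 lists "CGI baseline interview (overall and focused" at Baseline 2, day 29. No other CGI baseline interview appears in the protocol.

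**Day 113.** Protocol 4.1.1 lists "CGI-I (overall and focused" at the RCT end-of-treatment visit. RCT SAP 7.7.2.2 (Appendix 1 of the OLE SAP) ties this rating to day 29: "which is defined based on change relative to baseline evaluation at day 29".

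**OLE.** Neither Protocol 4.1.2 nor the Baseline OLE column of Appendix 1.2 has a CGI entry at the switch. The schedule row "CGI-I overall and focused" is marked at days 197 and 365 only.

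**General definition.** Protocol 3.2.2 describes the CGI-I as a judgement of how far the illness has improved or "worsened relative to a baseline state at the beginning of the intervention". It does not say whether, in the OLE, that means day 29 or day 113.

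**Analysis.** In the passive-active group, OLE SAP 7.8.4.3 tests whether "converted CGI-I scores after active tvCVS during the OLE are statistically significantly greater to those after passive treatment in the RCT". It converts the rating so that zero means no change, but does not say from when. OLE SAP 7.8.4 has the secondary endpoints follow the primary unless noted. The primary (7.8.2) compares the change over days 29 to 113 with the change over days 113 to 197.

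**The concern.** Most outcomes here are scores at a point in time, and a change for each period is obtained by subtracting the score at its start. A CGI-I rating cannot be re-based in this way, because the rater has already made the comparison with some earlier state. The state that the rater had in mind at day 197 therefore decides what the OLE test estimates.

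If it was day 113, the test compares two 12-week changes, as the primary endpoint does. If it was day 29, it compares a 24-week rating with a 12-week rating, and the passive-period response is not subtracted from the OLE change. If raters differed, the endpoint mixes the two.

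Overall CGI-I is fourth in the OLE testing order and gates MDS-UPDRS Part III and PDQ-39SI. Section 7.8.4.3 also turns significance on this test directly into a statement of clinical significance, with no separate threshold.

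**Working it through.** **Inputs from the documents.** Visit days 29, 113 and 197 (protocol schedules); 74 passive-active participants (OLE SAP 4); one-tailed tests at 0.05 (OLE SAP 7.8.2.1 and 7.8.4).

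**Assumptions.** The documents give no mean passive CGI-I change P and no SD for the paired CGI-I difference, so both are varied. Ratings are taken as additive: the rating over days 29 to 197 is the sum of the two period changes. A paired t-test stands in for the planned mixed model, as in the SAP's own OLE power calculation.

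**Plan's own figure.** OLE SAP 4 states power above 98% for a difference of 2.64, SD 5.32 and n = 74. With d = 2.64/5.32 = 0.496, the noncentral t gives 98.8% two-sided. The stated figure reproduces. The documents give no figure for CGI-I.

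**Spans.** (113 − 29)/7 = 12 weeks; (197 − 113)/7 = 12 weeks; (197 − 29)/7 = 24 weeks.

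**Contrast.** A is the mean change over days 113 to 197 on the converted scale.

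- Day 197 rated against day 113: A − P.
- Day 197 rated against day 29: (P + A) − P = A.

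Under the null that the secondary endpoints inherit from the primary (equal change in both periods, A = P), the first contrast has mean 0 and the second has mean P.

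**Rejection rate under A = P with a day-29 reference.** Noncentral t, 73 degrees of freedom, noncentrality P × √74 / SD:

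| Assumed SD | P = 0.1 | P = 0.2 | P = 0.3 | P = 0.5 |
|---|---|---|---|---|
| 0.8 | 28.1% | 68.6% | 94.0% | about 100% |
| 1.0 | 21.4% | 52.4% | 81.9% | 99.6% |
| 1.2 | 17.5% | 41.1% | 68.6% | 97.2% |
| 1.4 | 15.0% | 33.5% | 57.2% | 91.9% |

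With a day-113 reference the rate is 5% throughout.

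**Negative P.** If both periods show the same mean worsening of 0.2, the day-29 contrast has mean −0.2. At SD 1.0 the rejection rate is then 0.04%, so the test is harder to pass.

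**Check with whole-number ratings.** Simulation of 20,000 trials, period changes with SD 1.0, ratings rounded and limited to −3 to +3:

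| P | A | Day-29 reference | Day-113 reference |
|---|---|---|---|
| 0.2 | 0.2 | 45.7% | 5.3% |
| 0.3 | 0.3 | 73.7% | 4.8% |
| 0.5 | 0.5 | 98.2% | 4.6% |
| 0.3 | 0 | 4.1% | 0.0% |
| 0.5 | 0 | 3.9% | 0.0% |
| 0.5 | 0.25 | 56.9% | 0.1% |

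The rows with A = 0 show that a passive gain that is merely maintained is in both ratings and cancels. In the last row, an active period with half the passive-period gain still passes more often than not.

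**The case against.** The strongest reply is that the documents never say day 197 is rated against day 29, and that several provisions point to day 113. The passive-active group first receives active treatment at day 113, which fits the protocol's definition of the reference. OLE SAP 7.4 says: "Values obtained at the End of Treatment (EOT) visit for the RCT will define the OLE baseline values". Secondary endpoints follow the primary, which uses two separate 12-week changes. The protocol requires documented staff training on all assessments (1.1.5), and any rater instructions lie outside these documents. The empty Baseline OLE cell proves little by itself: most outcome measures are blank there, because the RCT end-of-treatment visit serves as OLE baseline. The RCT schedule also uses one CGI-I row label for both day 29 and day 113.

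Much of this stands. A reader might infer that the reference is known to stay at day 29, so that the test certainly sets 24 weeks against 12. The text is silent, and that is only one reading. A reader might also infer that the passive response is credited to the device. That is too strong, since a persisting gain cancels and the direction depends on the sign of P. Nor is CGI-I singled out by its wording. OLE SAP 7.8.4.1 has "For the passive-active group, the change from corresponding baseline to end of treatment", and the Part II section uses the same baseline wording, but the sections on MDS-UPDRS Part III and PDQ-39SI do not.

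The reply does not close the gap. The baseline rule works by subtraction. The CGI-I value obtained at day 113 is already a change from day 29, and 7.8.4.3 specifies no subtraction. The provisions show what contrast was probably intended, but no scheduled step records a CGI reference state at day 113 from which to make it.

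**Conclusion.** The concern holds as an undefined reference state, and it is more than a missing detail. The one reference interview that the schedule provides is at day 29, and using it gives a contrast that does not match the comparison set for the primary endpoint.

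On that reading the test is of A > 0 rather than A > P, a shift of exactly P in either direction. At SD 1.0 and A = P, rejection is about 52% at P = 0.2 and 82% at P = 0.3 instead of 5%. Across SD 0.8 to 1.4 and P from 0.1 to 0.5 it runs from 15% to about 100%. These figures are illustrations: P, the SD and additivity of a bounded ordinal rating are assumptions, and none of the figures applies if raters used day 113. The effect on the testing order arises only if the first three endpoints succeed.

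**What to change.** **Going forward.** At day 113, after the RCT CGI-I is scored, record a CGI reference state (overall and focused) from the same interview. Add it to the Baseline OLE column of the schedule. Instruct raters to judge day 197 against day 113, and state this in OLE SAP 7.8.4.3.

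**Ratings already made.** Establish and document, before analysis, which reference each rater used. Where it was day 29, report the contrast as incremental change only, not as active exceeding passive. A derived comparison may be added as a labelled sensitivity analysis: (day 197 minus day 113) against day 113, which equals day 197 minus twice day 113. Confine it to participants confirmed as rated against day 29. For anyone rated against day 113 it would give A − 2P, subtracting the passive response twice. It also counts day-113 rating error twice and relies on additivity.

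**Cost.** One form from an interview already held, one rater instruction and one SAP sentence. The real work is tracing the reference behind existing ratings; where it cannot be established, that should be reported.

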7.8.4.4. MDS-UPDRS Part III

The change in MDS-UPDRS Part III total score provides a measure of impact on motor signs in PD. This endpoint will be constructed, inclusive of imputation, as described in SAP v6.0 for RCT Study (Appendix 1). For the passive-active group, primary comparisons will be constructed using the MMRM model as previously described. Changes will be considered to be clinically meaningful if the mean difference exceeds the previously established MCID (-3.25 for clinical improvement) for this scale¹⁰.

7.8.4.5. PDQ-39SI

The PDQ39-SI will be calculated as described in the SAP v6.0 for RCT Study (Appendix 1). For the passive-active group, primary comparisons will be constructed using the MMRM model as previously described. Changes will be considered to be clinically meaningful if the mean difference exceeds the previously established MCID (-4.72 for clinical improvement) for this scale¹¹.

7.9. SAFETY ANALYSIS

7.9.1. Adverse Events (AEs)

Participants will be assessed for AEs every two weeks at minimum (either at study visits or during phone calls). For each group, the AEs will be summarized with frequency and percentage by preferred (PT) term, with all participants in that treatment group as the denominator. Classification will utilize MedDRA System Organ Class (SOC) based on MedDRA® Version 26.0 or other terminology/classification common to Parkinson's disease (e.g., falls, freezing of gait, etc.). AE incidence will be summarized by both severity and causal relationship to Device treatment (as determined by the blinded Principal Investigator or designated study personnel). AEs deemed to be of "possible" or "probable" relationship or "related" to the Device will also be considered as device related. AEs that occurred during the baseline period and post randomization will also be summarized. Additionally, the number of events and number of device-related events per person will be reported as a distribution.

The AE summary tables will provide an overall summary of AEs including the number and percentage of participants who experienced any AE, any SAE, any ADE, any SADE, any UADE, and any discontinuations in study participation due to an AE.

The objectives for the adverse event analysis in this study will be to confirm the safety/tolerability of tvCVS for the treatment of PD. For this, AE rates will be evaluated in the passive-active cohort. McNemar's test will be used to compare AE rates with tvCVS treatment during the first 12-week treatment period of the OLE as compared to AE rates during the passive treatment period in the RCT. Examination of the safety/tolerability of treatment periods longer than 12-weeks, will be evaluated as part of the procedures described within the appendices to this SAP.

7.10. EXPLORATORY ANALYSES

These exploratory endpoints have been added to support clinical applicability of the primary and secondary endpoints. They have been selected to provide additional detail that will impact decisions made by prescribing physicians and reimbursement entities.

Changes from baseline in the following assessments will be evaluated:

- 1. The Montreal Cognitive Assessment (MoCA)
- 2. The oral Symbol Digit Modality Test (oSDMT)
- 3. The Modified Schwab & England Activities of Daily Living Scale (S&E)
- 4. The Parkinson's Disease Sleep Scale-2 (PDSS-2)
- 5. The Epworth Sleepiness Scale (ESS)
- 6. The Functional Assessment of Chronic Illness Therapy-Fatigue Scale (FACIT-F)
- 7. The Geriatric Depression Scale (GDS)
- 8. The Parkinson's Anxiety Scale (PAS)
- 9. The Patient Reported Outcome Parkinson's Disease (PRO-PD). The PRO-PD collected at the study screen will be used as a practice-only and will not be included in the analysis as the scale's author has indicated that scores from the first completion of the assessment typically have high variability relative to the scores from subsequent administrations.
- 10. The MDS-NMS Non-Motor Fluctuations (NMF) Total Score
- 11. The Hoehn & Yahr score (H&Y)
- 12. Zarit Burden Interview (ZBI)
- 13. The Unified Parkinson's Disease Rating Scale Part I (UPDRS I)
- 14. The International Parkinson and Movement Disorder Society Unified Parkinson's Disease Rating Scale Part I: Non-Motor Aspects of Experiences of Daily Living (MDS-UPDRS Part I)
- 15. EncephaLogTM Finger Tapping Test the RCT baseline for this outcome will be the mean of scores collected weekly between Day 0 and Day 28.
- 16. EncephaLogTM 3m Timed Up and Go Test (3m TUG) Test the RCT baseline for this outcome will be the mean of scores collected weekly between Day 0 and Day 28.
- 17. EncephaLogTM 10m Timed Up and Go Test (10m TUG) This endpoint will evaluate the change in several measures related to the conduct of the 10-meter TUG at the end of the treatment period (day 113) relative to the baseline (day 29) including stride length, cadence, rotation time and time to complete.

For the primary comparison of interest (i.e. passive-active group following 12 weeks of treatment), the least-squares mean differences with corresponding 95% confidence intervals and p values will be constructed using the MMRM model discussed previously. However, no regulatory claims will be made in relation to these outcomes. Therefore, no adjustments will be made to address multiplicity of endpoints.

Treatment adherence, the Patient Global Impression of Improvement (PGI-I) and itemized answers from both the TNMTM Useability Questionnaire and the UPDRS IV assessment tool for the passive-active group will be reported descriptively. To further explore the effects of treatment on individual NMS, effects of treatment on each of the individual MDS-NMS domains will be evaluated. These domains include the following: (1) Depression, (2) Anxiety, (3) Apathy, (4) Psychosis, (5) Impulse control and related disorders, (6) Cognition, (7) Orthostatic hypotension, (8) Urinary, (9) Sexual, (10) Gastrointestinal, (11) Sleep and wakefulness, (12) Pain, and (13) Other. Only participants that demonstrate burden in the specified domain will be evaluated. In practice, this means that if any participant shows no burden on a given MDS-NMS domain throughout the study, then they will be excluded from this exploratory analysis.

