 - ii. Treatment Virtual visits 1 and 2 (day 141 and day 169 +/- 3 days)
 - Concomitant medication and adverse event review
 - MDS-NMS (does not include the NMF subscale)
 - Modified MDS-UPDRS Part III (excluding items related to rigidity and postural reflexes)

Virtual visits will be performed using the site's standard of care telemedicine platform.

- End of treatment visit 1(week 28/days 196, 197 or early termination)
 - i. ePROs (day 196 +/- 1 day) – to be completed in the on-state
 - PDQ-39
 - MDS-UPDRS Part II
 - GDS
 - PAS
 - PDSS-2
 - ESS
 - FACIT-F
 - ii. In clinic visit (day 197 +/- 3 days)
 - Concomitant medication and adverse event review
 - MDS-UPDRS Part III with video (captured using the Machine Medicine Kelvin software). *The timing of the administration of the MDS-UPDRS Part III from last DRT dose should be recorded and kept consistent with the timing from last dose to administration as noted in the BL2 visit. Administration must occur within 30 – 90 minutes after last dose.*
 - Mini-BESTest
 - 10m TUG (Encephalog™)
 - MDS-UPDRS Part I
 - MDS-NMS (includes the NMF subscale)
 - CGI-I (overall and focused)
 - S&E
 - PGI-I
 - Device Usability Questionnaire
 - Ear exam
 - MoCA v8.1

- UPDRS I
- UPDRS IV
- PRO-PD
- Zarit Burden Interview
- Conduct weight measurement
- Device return and supply return

Post-treatment observation: Participants will complete post-treatment follow up assessments at weeks 32 (days 224, 225), 38 (days 266, 267) and 44 (days 308, 309).

Phone Calls: (days 211, 224, 239, 253, 266, 281, 295, 308: +/- 1 day)

During phone calls scheduled every 2 weeks, study staff will review concomitant medications and potential adverse events.

- Follow-up Interim assessments 1 and 2 (week 32/days 224, 225 and week 38/days 266, 267)
 - i. ePROs (day 224 and day 266 +/- 1 day) – to be completed in the on-state
 - PDQ-39
 - MDS-UPDRS Part II
 - ii. Virtual visits (day 225 and day 267 +/- 3 days)
 - Concomitant medication and adverse event review
 - MDS-NMS (does not include the NMF subscale)
 - Modified MDS-UPDRS Part III (excluding items related to rigidity and postural reflexes)

Virtual visits will be performed using the site’s standard of care telemedicine platform.
- Follow up visit 3 (week 44/days 308, 309)
 - i. ePROs (day 308 +/- 1 day) – to be completed in the on-state
 - PDQ-39
 - MDS-UPDRS Part II
 - GDS
 - PAS
 - PDSS-2
 - ESS
 - FACIT-F
 - ii. In clinic visit (day 309 +/- 3 days)

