1. INTRODUCTION

This document describes the statistical analysis plan (SAP) for SNS-PD-003, the multicenter open label extension (OLE) study described in the protocol **Non-Invasive Brainstem Modulation for the Treatment of Non-Motor Symptoms in Parkinson's Disease: A Randomized Controlled Trial (RCT) and an Open Label Extension (OLE) Study** (Brief title: STEM-PD). This analysis plan is meant to supplement the study protocol and specifically refers to presentation of safety and efficacy analyses related to data collected through the first end of treatment (EOT1) period in the OLE on day 197 for the participants that received passive treatment during the RCT. Procedures related to SNS-PD-002, the preceding RCT study, are specified in a separate SAP (SAP v6.0 for RCT Study (ID: SNS-PD-002, NCT04797611), and the reader is referred to that document for all definitions of RCT specific measurements. Procedures related to exploratory analyses from SNS-PD-002 and SNS-PD-003, including data collected between days 197 and 365 in the OLE for the group that received passive treatment during the RCT, will be defined within appendices to this SAP. Any deviations from this analysis plan will be described in the clinical study report.

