7.8.2. Primary Endpoint and Comparison of Interest

The primary endpoint is the change in MDS-NMS total score at the end of treatment. The primary comparison is its change in MDS-NMS total score during the RCT treatment period (days 29-113) versus the change in MDS-NMS total score during the OLE treatment period 1 (days 113-197). This analysis of the primary comparison will only utilize the passive-active treatment group. The analysis will utilize data obtained during the RCT as well as data obtained from the OLE baseline and the twelve weeks of the OLE in which the participants will have been given the intervention.

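### OLE SAP 7.10 item 17 defines the 10-meter TUG change by RCT days only (day 113 versus day 29) and omits the active-period change to day 197

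*SAP*

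**What the plan says.** Item 17 in section 7.10 of the OLE SAP covers stride length, cadence, rotation time and time to complete. It defines the change in these measures as "10-meter TUG at the end of the treatment period (day 113) relative to the baseline (day 29", and names no other day.

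Other parts of the documents bear on how to read it:

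- **Day numbering.** OLE SAP 7.4 states that "all dates in this OLE SAP will be in reference to the first RCT visit (Day 0) as is specified in the protocol".
- **OLE baseline.** The same section says "Values obtained at the End of Treatment (EOT) visit for the RCT will define the OLE baseline values".
- **Comparison wanted.** For the primary endpoint, OLE SAP 7.8.2 compares the change "during the RCT treatment period (days 29-113") with the change "during the OLE treatment period 1 (days 113-197"), in the passive-active group only. For the exploratory endpoints, 7.10 asks for model-based mean differences "For the primary comparison of interest (i.e. passive-active group following 12 weeks of treatment").
- **Scope.** OLE SAP section 1 says the plan covers "data collected through the first end of treatment (EOT1) period in the OLE on day 197" for the participants who had passive treatment in the RCT.
- **Data collection.** Protocol 4.1.2 lists the 10m TUG under end of treatment visit 1, "In clinic visit (day 197 +/- 3 days"). The OLE schedule of events (Protocol Appendix 1.2) shows it at that visit and at no other.

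**The concern.** Item 17 is the only entry in the 7.10 list that fixes both ends of the change to particular days, and both are RCT days. In the passive-active group they bracket passive treatment. A programmer who implements the definition as written would compute the response to passive treatment and would never use the measurement taken after 12 weeks of active treatment.

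The wording is nearly the same as item 16 of RCT SAP 7.9, where days 29 and 113 are the right ones. Carry-over from that plan is the likely origin.

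Two things are at stake. Two competent analysts could produce different 10m TUG results from the same plan. And if the window is settled only after open-label data have been seen, the endpoint is no longer fully pre-specified. OLE SAP 7.10 presents these endpoints as support for prescribing and reimbursement decisions, so the definition should be unambiguous.

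**Working it through.** The plan gives no figure to reproduce here. The check is on visit days and on whether the required contrast can be formed.

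**1. Place the days on the study calendar (counted from RCT Day 0).**

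| Study day | Visit | 10m TUG scheduled? |
|---|---|---|
| 29 | RCT Baseline 2, in clinic | Yes |
| 113 | RCT end of treatment; also the OLE baseline | Yes |
| 197 | OLE end of treatment 1, in clinic | Yes, the only OLE visit |

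**2. Length of each window.**

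- Item 17: 113 − 29 = 84 days, which is the RCT treatment period in OLE SAP 7.8.2.
- OLE treatment period 1: 197 − 113 = 84 days. Item 17 does not mention it.

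**3. Treatment attached to the item 17 data.** OLE SAP 7.2 assigns each passive-active observation made before the first active treatment to passive treatment. Days 29 and 113 both come before it, so the item 17 change is wholly a passive-period change.

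**4. Could the days be on another scale?** OLE SAP 7.4 also defines an analysis day counted from study day 113. On that scale the item 17 days would be study days 113 + 29 = 142 and 113 + 113 = 226. These sit next to the virtual visits on days 141 and 225, where no 10m TUG is scheduled. This reading does not rescue the item.

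**5. Can the comparison in 7.10 be formed from the item 17 days?** Write X29, X113 and X197 for one participant's values.

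- Passive-period change: X113 − X29
- Active-period change: X197 − X113
- Within-participant difference: (X197 − X113) − (X113 − X29) = X197 − 2·X113 + X29

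All three days are needed. With days 29 and 113 alone, every passive-active record has ARM = 0 in the model of RCT SAP 7.7, which OLE SAP 7.8 adopts. The ARM coefficient, and so the passive-versus-active difference, cannot be estimated.

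**6. Size.** Item 17 covers four measures. OLE SAP section 4 expects 83 passive-arm completers and a further 10% attrition: 83 × 0.90 = 74.7, given there as 74 participants.

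**The case against.** The strongest reply is that the general rules already supply what item 17 omits. OLE SAP 7.10 requires a passive-versus-active difference for the listed endpoints. Section 7.8 sets out how active comparisons are handled within the passive-active arm, 7.2 assigns observations by treatment received, 7.4 makes day 113 the OLE baseline, and section 1 extends the plan to day 197. An analyst who tried to fit the model with only the item 17 change would find that the difference cannot be estimated, and would go back to the text. Items 15 and 16 also spell out only the RCT baseline and leave the OLE side to the general rules.

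Much of this stands. The intention to use OLE data is clear, and days 29 and 113 are not wrong days: they give the passive half, and day 113 is also the starting point of the active half. But the general rules contradict item 17 without correcting it. Items 15 and 16 name no end-of-treatment day and so leave room for the OLE period. Item 17 explicitly sets the end of treatment at day 113.

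A reader might infer more than this, in two ways that the documents do not support:

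- **That the whole OLE gait analysis rests on RCT data.** The 3m TUG (item 16) is not confined to RCT days, and the general rules show that active-period data were meant to enter.
- **That these are the only clinic gait measurements in the OLE.** MDS-UPDRS Part III, a gated secondary endpoint with items that RCT SAP 7.6.2 uses in its gait-difficulty score, and the mini-BESTest, a safety endpoint that covers gait, are both done in clinic at day 197.

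**Conclusion.** The point holds for item 17 as written. The endpoint definition states only the passive-period change and leaves out the active-period change ending at day 197, so it conflicts with the comparison in 7.10 and with the pattern set in 7.8.2. It is an internal contradiction in a stated rule, most likely carried over from the RCT SAP. It does not show that the sponsor means to report a passive response as an OLE result.

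The impact is low. It is confined to the four 10m TUG measures. OLE SAP 7.1 makes no statement of statistical significance for exploratory endpoints, and 7.10 makes no regulatory claim and no multiplicity adjustment for them. No endpoint in the testing hierarchy is touched.

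The conclusion rests on the day numbering in OLE SAP 7.4 and on the protocol schedule showing one OLE 10m TUG, at day 197. The figure of 74 participants is the plan's own expectation.

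**What to change.** Amend item 17 of OLE SAP 7.10 to say that, within the passive-active group, the active-period change in each 10m TUG measure (day 197 relative to day 113) will be compared with the passive-period change (day 113 relative to day 29).

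This brings the item into line with 7.4, 7.8.2 and the rest of 7.10. It costs one sentence: no new assessment, no change in sample size and no effect on any gated endpoint. It is best made before the OLE 10m TUG data are examined, so that the window is fixed in advance.
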